#### **8.4.1 SAE Reporting Requirements**

Participating investigators (all sites) must report all serious adverse events to the Sponsor within **24 hours** of discovery or notification of the event. The participating investigator must also provide follow-up information on the SAE until final resolution. Sponsor contact:

- [name], [[contact]](mailto:[contact]) and research coordinator, [name], [[contact]](mailto:[contact])

The Sponsor will review the SAE and report the event to the FDA, external collaborator(s), and IRB as applicable.

It is the Sponsor-Investigator's responsibility (e.g. lead site PI) to ensure that ALL serious adverse events that occur on the study (e.g. ALL SAEs that occur at each enrolling institution) are reported to all participating sites.

All SAEs should simultaneously be faxed or e-mailed to BMS at:

Global Pharmacovigilance & Epidemiology  
Bristol-Myers Squibb Company  
[contact]  
Email: [[contact]](mailto:[contact])

- An SAE report should be completed for any event where doubt exists regarding its seriousness.
- For studies with long-term follow-up periods in which safety data are being reported, include the timing of SAE collection in the protocol.
- If the investigator believes that an SAE is not related to study drug, but is potentially related to the conditions of the study (such as withdrawal of previous therapy or a complication of a study procedure), the relationship should be specified in the narrative section of the SAE Report Form.
- If only limited information is initially available, follow-up reports are required. (Note: Follow-up SAE reports should include the same investigator term(s) initially reported.)
- If an ongoing SAE changes in its intensity or relationship to study drug or if new information becomes available, a follow-up SAE report should be sent within 24 hours to BMS using the same procedure used for transmitting the initial SAE report. All SAEs should be followed to resolution or stabilization. All SAEs should be followed to resolution or stabilization.

**Institutional Review Board Reporting Requirements:**

Investigative sites will report adverse events to their respective IRB according to the local IRB's policies and procedures in reporting adverse events.

## 8.5 SAEs and OnCore

All SAEs will be entered into OnCore.

A copy of the SAE form(s) submitted to the sponsor-investigator is also uploaded into Oncore.

## 8.6 Data Safety and Toxicity Committee

It is the responsibility of each site PI to ensure that ALL SAEs occurring on this trial (internal or external) are reported to the Case Comprehensive Cancer Center's Data and Safety Toxicity Committee. This submission is simultaneous with their submission to the sponsor and/or other regulatory bodies.

The sponsor-investigator is responsible for submitting an annual report to the DSTC as per CCCC Data and Safety Monitoring Plan.

[figure not shown]
## 8.7 Data and Safety Monitoring Plan (DSMP)

This protocol will adhere to the policies of the Case Comprehensive Cancer Center Data and Safety Monitoring Plan in accordance with NCI guidelines.

## 9.0 PHARMACEUTICAL INFORMATION

A list of the adverse events and potential risks associated with the investigational or commercial agents administered in this study can be found in Section 8.

### 9.1 Decitabine (Dec)

Decitabine (Dec), NSC127716  
5-aza-2'-dexocytidine

#### 9.1.1 Product Description

Dec is manufactured by ScinoPharm (Tainan, Taiwan) and formulated by KP Pharmaceutical Technologies (Bloomington, IN, USA) as per current Federal Good Manufacturing Practice guidelines. Dec is supplied as capsules containing 5 mg of Dec per capsule, in bottles containing 8 capsules per bottle, together with a drying agent. Bottles should be tightly closed and stored in the refrigerator at 2-8°C. The label on the bottles includes the following information: the (i) name of the drug; (ii) quantity of drug per capsule; (iii) date of packaging; (iv) recommended storage temperature; (v) lot number of bulk drug used to generate the capsules.

### **9.1.2 Therapeutic Classification:**

DNA methyl-transferase enzymes (DNMTs) recognize and methylate target deoxycytidines that precede deoxyguanines (CpG), and are components of larger multi-protein complexes that mediate gene repression (silencing). Decitabine (Dec) is a deoxycytidine analogue with an unmodified deoxyribose and a single-base modification in the pyrimidine ring. This chemistry produces DNMT1-depletion without termination of DNA chain elongation or cytotoxicity within certain concentration ranges. The mechanism of action of Dec begins with uptake into cells, which involves membrane nucleoside transporters such as the human equilibrative nucleoside transporter (hENT1), followed by Dec phosphorylation, which is initiated by deoxycytidine kinase (DCK), then Dec nucleotide incorporation into the replicating genome. DNMT1 is covalently trapped, modified and depleted as it tries to methylate the 5-N position of the triazine ring of DNA-incorporated Dec. Replacement of 0.3% of cytidine in genomic DNA with Dec is sufficient to deplete 95% of DNMT1. Unlike cytidine analogues such as cytarabine or gemcitabine, the sugar back-bone of Dec is physiologic. Therefore, at low concentrations, Dec does not terminate DNA chain synthesis, and can deplete DNMT1 without causing significant DNA damage or cytotoxicity, both *in vitro* and *in vivo*. Low doses of Dec sufficient to deplete DNMT1 and produce hypomethylation do not overwhelm the cellular DNA-repair machinery, and although temporary growth arrest (cytostatic effect) may occur, cell division ultimately continues but with depleted DNMT1, DNA hypomethylation and consequently altered gene expression. At high Dec concentrations, hydrolytic cleavage at DNMT-CpG complexes overwhelms the cellular DNA-repair machinery, damaging the replicating genome to an extent that results in cell-death. Within cells, and at mucosal barriers and in the plasma, cytidine deaminase (CDA) is the enzyme most important in the break-down of Dec.

### **9.1.3 Method of Administration**

**- Starting dose of oral THU and Dec is by weight (all subsequent doses are based on the Cycle 1 Day 1 dose with dose modifications based on toxicities and tumor response as described in the protocol):**

*Weight 40-60kg* = 2 capsules of each drug. Dec capsules are ingested ~60 minutes after THU capsules.

*Weight 61-80kg* = 3 capsules of each drug. Dec capsules are ingested ~60 minutes after THU capsules.

*Weight 81-100kg or higher* = 4 capsules of each drug. Dec capsules are ingested ~60 minutes after THU capsules.

Subsequent dose changes should be based on hematologic parameters, non-hematologic toxicities attributed to study drug or as specified in the protocol.

**- Timing between THU and Dec:** Oral THU capsules followed ~60 minutes later by oral Dec capsules (oral Dec can be taken up to 6 hours after oral THU).

**- Frequency of THU and Dec ingestion:**

Oral THU ~10 mg/kg is administered 60 minutes before oral decitabine ~0.2 mg/kg 2X/week on consecutive days if there is no  $\geq$  grade 3 treatment-related non-hematologic toxicity and the ANC is  $>0.5 \times 10^9/L$  (if ANC is  $<0.5 \times 10^9/L$ , treatment is held until recovery above this threshold then resumed with a dose reduction as per Table 1).

[figure not shown]
- Patients will be required to have the treatment on the same consecutive days every week. If patients miss a dose they need they can make up the dose the same week ( $\pm 3$  days) and the study team needs to be notified.

**9.1.4 Storage requirements:** Capsules should be stored in the original bottles in which they are supplied in the refrigerator at 2-8°C.

**9.1.5 Drug Accountability:** The investigator or designated study personnel are responsible for maintaining accurate dispensing records of the study drug. All study drugs must be accounted for, including study drug accidentally or deliberately destroyed. Under no circumstances will the investigator allow the investigational drug to be used other than as directed by the protocol. If appropriate, drug storage, drug dispensing, and drug accountability may be delegated to the pharmacy section of the investigative site.

**9.1.6 Drug Destruction:** At the completion of the study, there will be a final reconciliation of drug shipped, drug consumed, and drug remaining. This reconciliation will be logged on the drug reconciliation form, signed and dated. Any discrepancies noted will be investigated, resolved, and documented prior to return of unused study drug. Unused drug is to be shipped back to source at completion of the study. Please contact [name], [name], [contact], email: [[contact]](mailto:[contact]) regarding shipping arrangements.

## 9.2 Tetrahydrouridine (THU)

3,4,5,6-Tetrahydrouridine, NSC112907  
2(1H)-pyrimidinone, tetrahydro-4-hydroxy-1-beta-D-ribofuranosyl

**9.2.1 Product description:** The THU is manufactured by ASH Stevens (Detroit, MI, USA) and formulated by KP Pharmaceutical Technologies (Bloomington, IN, USA) as per Federal Good Manufacturing Practice guidelines. THU is supplied as capsules containing 250 mg of THU per capsule, in bottles containing 8 capsules per bottle, together with a drying agent. Bottles should be tightly closed and stored in the refrigerator at 2-8°C. The

label on the bottles includes the following information: the (i) name of the drug; (ii) quantity of drug per capsule; (iii) date of packaging; (iv) recommended storage temperature; (v) lot number of bulk drug used to generate the capsules.

### **9.2.2 Therapeutic Classification**

Tetrahydrouridine (THU) is a competitive inhibitor of the pyrimidine metabolism enzyme cytidine deaminase (CDA) with  $K_i$  values of  $3-5 \times 10^{-8} M^{75,76}$ . The very high affinity of THU for CDA may be due to its resemblance to a tetrahedral intermediate of cytidine formed by addition of water across the 3,4 double bond. CDA binds THU approximately 4-orders of magnitude more tightly than uridine, the substrate for the reverse reaction catalyzed by CDA. However, slow onset of inhibition suggests that structural reorganization precedes the formation of a stable enzyme-inhibitor complex.

### **9.2.3 Dosing Information:**

**- Starting dose of oral THU and Dec is by weight (all subsequent doses are based on the Cycle 1 Day 1 dose with dose modifications based on toxicities and tumor response as described in the protocol):**

*Weight 40-60kg* = 2 capsules of each drug. Dec capsules are ingested ~60 minutes after THU capsules.

*Weight 61-80kg* = 3 capsules of each drug. Dec capsules are ingested ~60 minutes after THU capsules.

*Weight 81-100kg or higher* = 4 capsules of each drug. Dec capsules are ingested ~60 minutes after THU capsules.

Subsequent dose changes should be based on hematologic parameters, non-hematologic toxicities attributed to study drug or as specified in the protocol.

**- Timing between THU and Dec:** Oral THU capsules followed ~60 minutes later by oral Dec capsules (oral Dec can be taken up to 6 hours after oral THU).

**- Frequency of THU and Dec ingestion:**

Oral THU ~10 mg/kg is administered 60 minutes before oral decitabine ~0.2 mg/kg 2X/week on consecutive days if there is no  $\geq$  grade 3 treatment-related non-hematologic toxicity and the ANC is  $>0.5 \times 10^9/L$  (if ANC is  $<0.5 \times 10^9/L$ , treatment is held until recovery above this threshold then resumed with a dose reduction as per Table 1).

- Patients will be required to have the treatment on the same consecutive days every week. If patients miss a dose they need they can make up the dose the same week ( $\pm 3$  days) and the study team needs to be notified.

**9.2.4 Storage requirements:** Capsules should be stored in the original bottles in which they are supplied in the refrigerator at 2-8°C.

**9.2.5 Drug Accountability:** The investigator or designated study personnel are responsible for maintaining accurate dispensing records of the study drug. All study drugs must be accounted for, including study drug accidentally or deliberately destroyed. Under no

circumstances will the investigator allow the investigational drug to be used other than as directed by the protocol. If appropriate, drug storage, drug dispensing, and drug accountability may be delegated to the pharmacy section of the investigative site.

**9.2.6 Drug Destruction:** At the completion of the study, there will be a final reconciliation of drug shipped, drug consumed, and drug remaining. This reconciliation will be logged on the drug reconciliation form, signed and dated. Any discrepancies noted will be investigated, resolved, and documented prior to return of unused study drug. Unused drug is to be shipped back to source at completion of the study. Please contact [name], [name], [contact], email: [[contact]](mailto:[contact]) regarding shipping arrangements.

### **9.3 Nivolumab**

Nivolumab (Opdivo™) is manufactured by Bristol Myers Squibb (New Jersey, USA) as per Federal Good Manufacturing Practice guidelines. It is FDA approved for use in metastatic NSCLC. The drug for the study will be provided by Bristol Myers. See section 1.4 and 6.1 for details on the drug and dosing.

**PRODUCT INFORMATION TABLE:** Please also see Drug Information in Investigators brochure

Product Description:(Other names = MDX-1106, ONO-4538, anti-PD-1)					
Product Description and Dosage Form	Potency	Primary Packaging (Volume)/ Label Type	Secondary Packaging (Qty) /Label Type	Appearance	Storage Conditions (per label)
Nivolumab (BMS-936558-01)* Injection drug product is a sterile, non-pyrogenic, single-use, isotonic aqueous solution formulated at 10 mg/mL	100 mg/Vial (10 mg/mL).	Carton of 5 or 10 vials	10-cc Type 1 flint glass vials stoppered with butyl stoppers and sealed with aluminum seals.	Clear to opalescent, colorless to pale yellow liquid. May contain particles	BMS-936558-01 Injection must be stored at 2 to 8 degrees C (36 to 46 degrees F) and protected from light and freezing

\*Nivolumab may be labeled as BMS-936558-01 Solution for Injection

If stored in a glass front refrigerator, vials should be stored in the carton. Recommended safety measures for preparation and handling of nivolumab include laboratory coats and gloves.

For additional details on prepared drug storage and use time of nivolumab under room temperature/light and refrigeration, please refer to the BMS-936558 (nivolumab) Investigator Brochure section for “Recommended Storage and Use Conditions”

### **Handling and Dispensing**

The investigator should ensure that the study drug is stored in accordance with the environmental conditions (temperature, light, and humidity) as per product information and the Investigator Brochure and per local regulations. It is the responsibility of the investigator to ensure that investigational product is only dispensed to study subjects. The investigational product must be dispensed only from official study sites by authorized personnel according to local regulations. If concerns regarding the quality or appearance of the study drug arise, the study drug should not be dispensed and contact BMS immediately.

Please refer to the current version of the Investigator Brochure and/or shipment reference sheets for additional information on storage, handling, dispensing, and infusion information for nivolumab.

### **Destruction**

Sponsor/Investigator drug destruction is allowed provided the following minimal standards are met:

- On-site disposal practices must not expose humans to risks from the drug.
- On-site disposal practices and procedures are in agreement with applicable laws and regulations, including any special requirements for controlled or hazardous substances.
- Written procedures for on-site disposal are available and followed. The procedures must be filed with the Sponsor SOPs and a copy provided to BMS upon request.
- Records are maintained that allow for traceability of each container, including the date disposed of, quantity disposed, and identification of the person disposing the containers. The method of disposal, ie, incinerator, licensed sanitary landfill, or licensed waste disposal vendor must be documented.
- Accountability and disposal records are complete, up-to-date, and available for BMS to review throughout the clinical trial period as per the study agreement.

If conditions for destruction cannot be met, please contact BMS.

It is the Sponsor Investigator’s responsibility to arrange for disposal of all empty containers, provided that procedures for proper disposal have been established according to applicable federal, state, local, and institutional guidelines and procedures, and provided that appropriate records of disposal are kept.

### **Dose calculations and administration**

Describe timing of first dose from registration/randomization. For preparation and administration details please refer to the current Investigator Brochure.

Nivolumab will be given every two weeks at a dose of 240mg IV flat dose to be administered as a 60 minute IV infusion.

Subjects may be dosed no less than 12 days from the previous dose of drug. There are no premedications recommended for nivolumab on the first cycle.

The dosing calculations should be based on the actual body weight at baseline. If the subject's weight on the day of dosing differs by > 10% from the weight used to calculate the original dose, the dose must be recalculated. All doses should be rounded to the nearest milligram. There will be no dose modifications allowed.

Subjects should be carefully monitored for infusion reactions during nivolumab administration. If an acute infusion reaction is noted, subjects should be managed according to Protocol Section 6.1. Doses of nivolumab may be interrupted, delayed, or discontinued depending on how well the subject tolerates the treatment.

Nivolumab Injection, 100 mg/10 mL (10 mg/mL) and 40 mg/mL (10 mg/mL) Nivolumab injection is to be administered as an IV infusion through a 0.2-micron to 1.2-micron pore size, low-protein binding polyethersulfone membrane in-line filter at the protocol-specified doses. It is not to be administered as an IV push or bolus injection. Nivolumab injection can be infused undiluted (10 mg/mL) or diluted with 0.9% Sodium Chloride Injection, USP or 5% Dextrose Injection, USP to protein concentrations as low as 1 mg/mL. Care must be taken to assure sterility of the prepared solution as the product does not contain any antimicrobial preservative or bacteriostatic agent.

### **Dose Modifications**

Dose reductions or dose escalations are not permitted.

### **Management Algorithms**

Guidelines for the management of immune related events can be found in the current Investigator Brochure AND in the approved USPI in the US. Investigators should decide the appropriate source of AE management for each protocol.

Immuno-oncology (I-O) agents are associated with AEs that can differ in severity and duration than AEs caused by other therapeutic classes. Nivolumab is considered an immuno-oncology agent in this protocol. Early recognition and management of AEs associated with immuno-oncology agents may mitigate severe toxicity. Management algorithms have been developed to assist investigators in assessing and managing the following groups of AEs:

Gastrointestinal, Renal, Pulmonary, Hepatic, Endocrinopathies, Skin, Neurological.

For subjects expected to require more than 4 weeks of corticosteroids or other immunosuppressants to manage an AE, consider recommendations provided in the algorithms. These algorithms are found in the Nivolumab IB [and in Appendix] of this protocol. The guidance provided in these algorithms should not replace the Investigator's medical judgment but should complement it.

### **Discontinuation Criteria**

Treatment should be permanently discontinued for the following:

- Any Grade 2 drug-related uveitis or eye pain or blurred vision that does not respond to topical therapy and does not improve to Grade 1 severity within the re-treatment period OR requires systemic treatment
- Any Grade 3 non-skin, drug-related adverse event lasting > 7 days, with the following exceptions for drug-related laboratory abnormalities, uveitis, pneumonitis, bronchospasm, hypersensitivity reactions, and infusion reactions, and endocrinopathies:
  - Grade 3 drug-related uveitis, pneumonitis, bronchospasm, hypersensitivity reaction, or infusion reaction of any duration requires discontinuation
  - Grade 3 drug-related endocrinopathies adequately controlled with only physiologic hormone replacement do not require discontinuation
  - Grade 3 drug-related laboratory abnormalities do not require treatment discontinuation except those noted below
    - Grade 3 drug-related thrombocytopenia > 7 days or associated with bleeding requires discontinuation
    - Any drug-related liver function test (LFT) abnormality that meets the following criteria require discontinuation:
      - AST or ALT > 8 x ULN
      - Total bilirubin > 5 x ULN
      - Concurrent AST or ALT > 3 x ULN and total bilirubin > 2 x ULN
- Any Grade 4 drug-related adverse event or laboratory abnormality, except for the following events which do not require discontinuation:
  - Isolated Grade 4 amylase or lipase abnormalities that are not associated with symptoms or clinical manifestations of pancreatitis and decrease to < Grade 4 within 1 week of onset.
  - Isolated Grade 4 electrolyte imbalances/abnormalities that are not associated with clinical sequelae and are corrected with supplementation/appropriate management within 72 hours of their onset

- Grade 4 lymphopenia or leucopenia
- Grade 4 drug-related endocrinopathy adverse events, such as adrenal insufficiency, ACTH deficiency, hyper- or hypothyroidism, or glucose intolerance, which resolve or are adequately controlled with physiologic hormone replacement (corticosteroids, thyroid hormones) or glucose-controlling agents, respectively, may not require discontinuation after discussion with and approval from the Investigator
- Any dosing interruption lasting > 6 weeks with the following exceptions:
  - Dosing delays or interruptions to allow for prolonged steroid tapers to manage drug-related adverse events are allowed. Prior to re-initiating treatment in a subject with a dosing interruption lasting > 6 weeks, the Investigator must be consulted. Tumor assessments should continue as per protocol even if dosing is interrupted or delayed
  - Dosing interruptions or delays lasting > 6 weeks that occur for non-drug-related reasons may be allowed if approved by the Investigator. Prior to re-initiating treatment in a subject with a dosing interruption lasting > 6 weeks, the Investigator must be consulted. Tumor assessments should continue as per protocol even if dosing is interrupted
- Any adverse event, laboratory abnormality, or intercurrent illness which, in the judgment of the Investigator, presents a substantial clinical risk to the subject with continued nivolumab dosing
  - Treatment beyond radiographic progression is allowed if it is felt by the investigators that there is clinical benefit. If new or pre-existing asymptomatic brain lesions are noted on surveillance MRI. These patients need to be followed closely with follow up brain imaging on treatment and can receive gamma knife therapy while actively receiving therapy on study – study drugs do not require disruption while receiving gamma knife therapy unless clinically indicated to do so. Use of steroids after Gamma knife therapy should be minimized but can be used per clinical discretion of the treating radiation oncologist.

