**7.3 Dose Modification or dose delay of Nivolumab**

No Dose modification for nivolumab is suggested. Because of the potential for clinically meaningful nivolumab-related AEs requiring early recognition and prompt intervention,

management algorithms have been developed for suspected AEs of selected categories. See Appendix III

Dose delay criteria apply for all drug-related adverse events (regardless of whether or not the event is attributed to nivolumab). If AE is felt to be immune related and attributable to nivolumab, if the patient is on the study arm they can continue THU-Dec while nivolumab is held.

Dose delay criteria apply for all drug-related AEs. Nivolumab must be delayed until treatment can resume

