**Criteria to Resume Treatment**

Subjects may resume treatment with study drug when the drug-related AE(s) resolve to Grade  $\leq 1$  or baseline value, with the following exceptions:

- Subjects may resume treatment in the presence of Grade 2 fatigue
- Subjects who have not experienced a Grade 3 drug-related skin AE may resume treatment in the presence of Grade 2 skin toxicity
- Subjects with baseline Grade 1 AST/ALT or total bilirubin who require dose delays for reasons other than a 2-grade shift in AST/ALT or total bilirubin may resume treatment in the presence of Grade 2 AST/ALT OR total bilirubin
- Subjects with combined Grade 2 AST/ALT AND total bilirubin values meeting discontinuation parameters should have treatment permanently discontinued

- Drug-related pulmonary toxicity, diarrhea, or colitis, must have resolved to baseline before treatment is resumed. *Subjects with persistent Grade 1 pneumonitis after completion of a steroid taper over at least 1 month may be eligible for retreatment.*
- Drug-related endocrinopathies adequately controlled with only physiologic hormone replacement may resume treatment.

If the criteria to resume treatment are met, the subject should restart treatment at the next scheduled timepoint per protocol. However, if the treatment is delayed past the next scheduled timepoint per protocol, the next scheduled timepoint will be delayed until dosing resumes.

If treatment is delayed or interrupted for > 6 weeks, the subject must be permanently discontinued from study therapy, except as specified in discontinuation section.

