### Potential Drug Induced Liver Injury (DILI)

Wherever possible, timely confirmation of initial liver-related laboratory abnormalities should occur prior to the reporting of a potential DILI event. All occurrences of potential DILIs, meeting the defined criteria, must be reported as SAEs. Potential drug induced liver injury is defined as:

- 1) ALT or AST elevation > 3 times upper limit of normal (ULN)  
AND
- 2) Total bilirubin > 2 times ULN, without initial findings of cholestasis (elevated serum alkaline phosphatase)  
AND
- 3) No other immediately apparent possible causes of AST/ALT elevation and hyperbilirubinemia, including, but not limited to, viral hepatitis, pre-existing chronic or acute liver disease, or the administration of other drug(s) known to be hepatotoxic.

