# Hepatic Adverse Event Management Algorithm

Rule out non-inflammatory causes. If non-inflammatory cause, treat accordingly and continue I-O therapy. Consider imaging for obstruction.

[figure not shown]
Patients on IV steroids may be switched to an equivalent dose of oral corticosteroids (e.g. prednisone) at start of tapering or earlier, once sustained clinical improvement is observed. Lower bioavailability of oral corticosteroids should be taken into account when switching to the equivalent dose of oral corticosteroids.

\*I-O therapy may be delayed rather than discontinued if AST/ALT ≤ 8 x ULN and T.bili ≤ 5 x ULN.

\*\*The recommended starting dose for grade 4 hepatitis is 2 mg/kg/day methylprednisolone IV.

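### Section 9.3 requires a permanent stop of nivolumab for a combined liver-test elevation that the Appendix III hepatic footnote allows to be managed by delay

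*Combined protocol and SAP*

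**What the plan says.** Section 9.3, Discontinuation Criteria, is directive: "Any drug-related liver function test (LFT) abnormality that meets the following criteria require discontinuation". Three criteria follow: AST or ALT above 8 x ULN; total bilirubin above 5 x ULN; or "Concurrent AST or ALT > 3 x ULN and total bilirubin > 2 x ULN".

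The Hepatic Adverse Event Management Algorithm in Appendix III is a flowchart that is not shown in the available text. Its footnote is readable: "I-O therapy may be delayed rather than discontinued if AST/ALT ≤ 8 x ULN and T.bili ≤ 5 x ULN".

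Section 7.3 directs sites to that appendix for nivolumab events: "management algorithms have been developed for suspected AEs of selected categories. See Appendix III". Its Criteria to Resume Treatment contain a general permission, "Subjects may resume treatment with study drug when the drug-related AE(s) resolve to Grade" 1 or less or to baseline, and a specific bar: "Subjects with combined Grade 2 AST/ALT AND total bilirubin values meeting discontinuation parameters should have treatment permanently discontinued".

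Section 8.2.2 uses the same numerical limits (above 3 x for AST or ALT, above 2 x for bilirubin) to define potential drug-induced liver injury, and makes it reportable: "All occurrences of potential DILIs, meeting the defined criteria, must be reported as SAEs".

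**The concern.** Both texts answer the same question, delay or discontinue, and share the 8 x and 5 x limits. The footnote leaves out the combined criterion. A clinician managing hepatitis from the appendix could therefore hold nivolumab in a patient for whom Section 9.3 requires a permanent stop, and could restart it once the tests recover. That would be re-exposure after a pattern the protocol itself treats as possible drug-induced liver injury. Two patients with identical results could also be handled differently, depending on which page the site opened.

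**Working it through.** No sample size, power or event rate enters this point. The check compares two threshold rules.

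**Inputs.** Let A be AST or ALT and B be total bilirubin, both in multiples of ULN, for a drug-related abnormality. Section 9.3 has no stop rule for liver tests that are not drug-related.

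- Stop (Section 9.3): A > 8, or B > 5, or (A > 3 and B > 2).
- Delay permitted (Appendix III footnote as printed): A ≤ 8 and B ≤ 5.

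**Overlap.** The delay condition rules out the first two stop criteria, so only the third can coincide with it. Both rules apply when 3 < A ≤ 8 and 2 < B ≤ 5.

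**Cases.** These points were chosen to test the boundaries. They say nothing about how often such values occur.

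| A | B | Section 9.3 | Footnote | Result |
|---|---|---|---|---|
| 3.1 | 2.1 | stop | delay permitted | conflict |
| 6 | 4 | stop | delay permitted | conflict |
| 8 | 5 | stop | delay permitted | conflict |
| 3 | 2 | no stop | delay permitted | agree |
| 6 | 1.5 | no stop | delay permitted | agree |
| 2.5 | 4 | no stop | delay permitted | agree |
| 8.1 | 1 | stop | no permission | agree |
| 2 | 5.1 | stop | no permission | agree |
| 9 | 6 | stop | no permission | agree |

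All three conflicting cases also exceed the numerical limits for potential liver injury in Section 8.2.2.

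**Does any text rank the two?**

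- The opening of Appendix III describes its content as general guidance to the investigator. That lowers its standing but does not mention Section 9.3.
- Section 9.3, Management Algorithms, sets the algorithms beside medical judgment, not beside the discontinuation list. It also leaves the source of event management (Investigator Brochure or US label) to investigators.
- The specific bar in Section 7.3 supports Section 9.3, but its words name combined Grade 2 values only. Reading it as more lenient for worse values would be implausible, yet the wording does not close the gap.

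**What follows a hold?** The general permission in Section 7.3 allows treatment to restart on recovery. The six-week limit on interruptions would not reliably turn a hold into a stop, because Section 9.3 allows longer interruptions for prolonged steroid tapers.

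**Do the reporting rules settle it?** Section 8.4.1 requires serious adverse events to reach the sponsor within 24 hours. Sections 8.2.2 and 8.4.1 govern reporting, not dosing. The Section 8.2.2 definition is also narrower than the Section 9.3 criterion: it requires "Total bilirubin > 2 times ULN, without initial findings of cholestasis (elevated serum alkaline phosphatase"), and no other immediately apparent cause.

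**Check of the amendment.** With the footnote changed to A ≤ 8 and B ≤ 5 and not (A > 3 and B > 2), the intersection with the stop rule is empty. The three conflicting cases become stop only, and the other six are unchanged.

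**The case against.** The strongest objection is that the footnote hangs on an asterisk in a flowchart nobody can see here. If the marked box deals only with single-test elevations, or a neighbouring box already handles the combined one, the conflict shrinks or disappears. This stands as a limit: the finding is about the footnote as printed, and the flowchart must be checked before the text is changed.

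The second objection is that ordinary reading already settles the order. Section 9.3 is specific and mandatory; the appendix is generic guidance in permissive terms; and Section 7.3, which points to the appendix, also contains a permanent-stop rule for combined elevations. This is largely right. Section 9.3 is the more natural governing text, and a site that stops complies with both. But a fixed stopping threshold should not depend on inference when another part of the protocol expressly permits the less cautious action.

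Third, the sentence on choosing a source of event management concerns the Investigator Brochure and the US label, not a choice between Section 9.3 and the appendix. That is fair. The sentence is weak evidence, and the finding does not need it.

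Finally, serious-event reporting and the separate Section 9.3 stop for substantial clinical risk, at the investigator's judgment, limit the harm. They do, and they keep the severity low. Neither replaces the fixed threshold.

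**Conclusion.** The inconsistency holds as a minor safety point. It is confined to drug-related abnormalities with AST or ALT above 3 and up to 8 x ULN together with bilirubin above 2 and up to 5 x ULN. Outside that region the two texts agree. The number of patients affected cannot be estimated, because the documents give no rate for such events. The nivolumab rules are the same in both arms, and the response endpoint, alpha, power and two-stage rule are unaffected. The conclusion assumes that the unseen flowchart does not already except the combined elevation. Confidence is medium for that reason.

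**What to change.** Add to the Appendix III hepatic footnote: *unless AST or ALT above 3 x ULN and total bilirubin above 2 x ULN are concurrent, in which case discontinue per Section 9.3.*

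Add to Sections 7.3 and 9.3: *Where Section 9.3 requires discontinuation, a permission to delay in Appendix III does not apply. Any stricter instruction in the algorithms still applies.*

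Before adopting either, the sponsor should check the wording against the full hepatic flowchart. It should also confirm that the second sentence of the note does not turn guidance boxes into binding rules unintentionally. The Section 9.3 criteria stay as they are. The cost is one clause and a two-sentence note; neither calls for extra patients, visits or tests, subject to that check.
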